Oficial title

Polypectomy With Hot vs Cold Snare in Small Colonic Lesions

• Valladolid (Spain), 17 November 2018

Abstract

Colonoscopy is the technique of choice for the diagnosis and prevention of colorectal cancer (CRC). The identification and extirpation of adenomas decreases the incidence of CRC by up to 76%. More than 70% of the excised lesions are less than 10 mm. There is controversy about the technique to be used (resection with cold vs hot snare) in the lesions of 5-9mm. Both use a polypectomy snare, differing in that the cold handle cuts by friction, while the hot snare uses electrical current. We propose a multicentre randomized clinical trial comparing both endoscopic techniques. At least 394 injuries per group will be included, randomizing patients to whom a diagnostic colonoscopy is requested for symptoms, screening or revision protocols. Randomization will be performed stratified by endoscopist. The primary objective is the proportion of incomplete polypectomies, which will be analyzed centrally from random biopsies of the edges of the lesion. As secondary objectives, we will compare the proportion of immediate and delayed hemorrhagic complications, the evolution of postprocedural abdominal pain and the factors associated with incomplete excision in each group and the factors associated with a failed cold polypectomy. The analysis of the primary objective will be carried out by means of the z test of homogeneity without using the correction of Yates, estimating the confidence interval of the difference between both groups. The analysis will be carried out by intention to treat and by protocol.

1. Introduction

Colorectal cancer (CRC) is a major cause of morbidity and mortality worldwide. It is estimated that in 2008, 1233,000 new cases were diagnosed and more than 600,000 people died for this reason throughout the world (1). Colonoscopy is the technique of choice for both diagnosis and prevention (2), since the identification and removal of colonic adenomas reduces the incidence of CRC by up to 76% (3-7).

Different endoscopic techniques have been developed for the removal of adenomas; The choice of some over others is made according to the size, morphology and location of the lesion.

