The evaluation of the resections can be done by several methods, which conditions the disparity observed in the different works. The ideal method would be the evaluation of the margins of lateral and vertical resection. However, this is complicated by the usual handling of the samples (fragmented samples, samples submitted for histological study in pot instead of mounted ...), so the number of non-valuable samples can reach 40% (11). Another option is to take biopsies from the edges of the lesion. Although it includes a component of subjectivity, depending on where the biopsies are taken, it allows to evaluate all the injuries. In 2010, Pohl et al published a paper based on data from 2 North American centers (12). All resections were made with hot loop, being incomplete in 6.8% of the lesions <10 mm. The cold loop technique presents similar results. In a study in which 59 slightly smaller polyps were analyzed (average size 3.7 mm), incomplete resections were observed in 6.8% (13). The studies in which the edges of resection are evaluated show greater proportions in both techniques. The work published in 2015 by Din and colleagues, comparing two techniques of cold cutting in lesions of 3-7 mm, observed a proportion of incomplete polypectomies close to 30% (14) while another retrospective observational work with 175 lesions of 3-10 mm extirpated with cold snare and 1010 of 6-15 mm excised with hot snare, the proportion of histologically complete polypectomies was 53% and 61%, respectively (15).

2. Hypothesis

Conceptual hypothesis:

Cold snare polypectomy presents a proportion of incomplete polypectomies similar to polypectomy with hot snare.

Operational hypothesis:

Two endoscopic techniques will be compared from two groups created by a random assignment to one or another type of polypectomy, evaluating the proportion of non-excised polypoid tissue after it. This will be done from random biopsies of the edges of the lesion and possible macroscopic remnants

3. Objectives.

Primary objective:

To compare the proportion of incomplete polypectomies in both types of polypectomy (cold snare vs. hot snare).

Secondary objectives:

- ²Compare the proportion of immediate and delayed bleeding complications, total and according to the severity that they present according to the ASGE classification.
- ² Compare the evolution of abdominal pain in the 5 hours postprocedure between both groups.

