Assuming a proportion of incomplete polypectomies in both groups of 10% (using the taking of biopsies as a diagonostic pattern) and setting an equivalence limit of 7%, a total of 315 lesions per group are estimated to have an α risk of 5% and a power of 80%. Assuming a proportion of losses (polyps not recovered for histological study, polypectomies of the failed Cold group of 20%), an estimated 394 lesions per group are needed, with a total of 788 lesions in total.

Data Collect

All the variables concerning the characteristics of the endoscopist, the patient and the injuries included will be collected in each center. The variables related to the histological diagnosis will be collected in the same way in the respective center. The variables concerning the follow-up will be collected in a centralized manner, through a telephone call that will be made between 3 and 4 weeks from the procedure. The variable related to the histological study of the base of the polyp will be collected in a centralized manner by the pathologist in charge of the analysis of the samples.

6. Data management

Data from the data collection notebooks will be merged by the main researcher or collaborating researchers anonymously, encrypted and dissociated from the clinical information by means of a patient identification code (ID), in a database made through the program Access (Microsoft Corporation, Redmond, WA USA). A copy of the database will be used in each participating center, which will be merged after completing the data collection. The responsible researcher will define an ID for each participant. The data entered in the

database will be anonymous and the database will be protected with a password to which only the researchers will have access.

The unified file will be kept at the Río Hortega University Hospital and will be maintained until the end of the study. Regarding the application of the Organic Law on Data Protection 15/1999 and Royal Decree 1720/2007 that develops it, it should be noted that the protocol defined in the project oriented to epidemiological analysis, determines that the files will record information completely anonymized

7. Statistical analysis

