The Access program (Microsoft Corporation, Redmond, WA USA) will be used for the realization of the database and the statistical analysis of them will be carried out through the STATA program (StataCorp, 2013. Stata Statistical Software: Release 13. College Station, TX: StataCorp LP). In the quantitative variables, the arithmetic mean and the standard deviation will be calculated (variables that do not follow a normal distribution according to the Kolmogorov-Smirnov test will be described with median, minimum, maximum and interquartile range), and the qualitative ones will be expressed as percentages and your 95% confidence intervals.

The analysis of the primary objective, the proportion of incomplete polypectomies in both groups will be compared by means of the z test of homogeneity without using the correction of Yates. The confidence interval of the difference between the two groups will also be estimated. The analysis will be carried out by intention to treat, regardless of the type of polypectomy performed and per protocol (assigning the lesions assigned to the group Cold that are extirpated with hot snare to the Hot group). To evaluate possible confounding factors (endoscopist, nurse, handle type, location ...), the STATA confound user command will be used, defining as a significant change that which conditions a change in the odds ratio greater than 10% with respect to the one obtained with the complete model. In case several models do not present differences greater than 10%, the most parsimonious will be chosen.

Within the secondary objectives, the proportion of complications in both groups will be verified by the de2 test. To evaluate the factors associated with incomplete polypectomies and those associated with failed cold polypectomy, multivariate logistic regression techniques will be used.

8. Ethical aspects

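### The trial is sized for equivalence within 7 percentage points, but its primary test is a z test of equality, and no confidence level or decision rule ties the planned interval to the 7% limit.

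*Combined protocol and SAP*

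**What the plan says.** - **Section 2, conceptual hypothesis:** "Cold snare polypectomy presents a proportion of incomplete polypectomies similar to polypectomy with hot snare".
- **Section 5, Sample size:** with 10% incomplete polypectomies expected in both groups, an α risk of 5% and 80% power, the text reads "setting an equivalence limit of 7%, a total of 315 lesions per group are estimated". Allowing for 20% losses gives 394 per group, 788 in total.
- **Section 7, primary analysis:** the proportions "will be compared by means of the z test of homogeneity without using the correction of Yates". It then adds: "The confidence interval of the difference between the two groups will also be estimated".
- **Abstract:** the same plan, a "z test of homogeneity without using the correction of Yates, estimating the confidence interval of the difference between both groups".
- **Confidence level:** the only one in section 7 is for descriptive statistics, where "the qualitative ones will be expressed as percentages and your 95% confidence intervals".

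The 7% limit appears only in the sample size paragraph. Neither the abstract nor section 7 mentions it, gives a level for the interval of the difference, or says which result would support similarity.

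**The concern.** The sample size answers one question (are the two techniques within 7 points of each other?) and the named primary test answers another (is there evidence that they differ?). A test of homogeneity can reject equality. It cannot establish similarity, because failure to reject may only reflect limited precision.

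The interval of the difference could carry the equivalence claim, but only with a level and a comparison with the limit, and the plan gives neither. The rule for the main conclusion would then be settled after the data are seen. It is also open whether a non-significant z test would be reported as similarity, and whether the planned 80% power applies to the interval eventually used.

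**Working it through.** **Inputs** (section 5, Sample size): p = 0.10 in both groups, limit m = 0.07, α = 5%, power 80%, losses 20%. Section 5, Randomization, gives 1:1 allocation. Assumptions added here: the z test is two-sided at 5% (no level is stated), and lesions are independent. The document writes the limit without a sign; ±7 is inferred from the word equivalence and from step 1.

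**1. Reproduce the plan's figure.** For two one-sided tests with a true difference of zero:

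n = 2p(1-p)(z₁₋α + z₁₋β/₂)² / m² = 2 × 0.1 × 0.9 × (1.645 + 1.282)² / 0.07² = 314.6 (unrounded quantiles), so **315**. Then 315 / 0.8 = 393.75, so **394**. Both match.

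**2. Other designs do not give 315.**

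| Design (80% power) | n per group |
|---|---|
| Two one-sided 5% tests | 314.6 |
| Two one-sided 2.5% tests | 386.0 |
| Non-inferiority, one-sided 5% | 227.1 |
| Non-inferiority, one-sided 2.5% | 288.3 |
| z test of equality, 10% vs 17% | 372.9 |
| z test of equality, 10% vs 3% | 193.5 |

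The trial was therefore sized for equivalence at 5% per side, which corresponds to a two-sided 90% interval.

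**3. Power depends on the missing level.** With both arms at 10%, power ≈ 2Φ(m/SE - z) - 1, where SE = √(2 × 0.1 × 0.9 / n). At n = 315, SE = 0.0239 and m/SE = 2.93. With z = 1.645 this gives 80.1%; with z = 1.960 it gives 66.7%. Exact enumeration of two independent binomials (Wald interval) gives:

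| Interval | 315 per group | 394 per group |
|---|---|---|
| 90% within ±7 | 80.1% | 89.5% |
| 95% within ±7 | 66.9% | 81.0% |

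**4. Results for which the plan gives no conclusion.** Same enumeration, both arms at 10%, pooled z test non-significant but interval not wholly within ±7:

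| Interval | 315 per group | 394 per group |
|---|---|---|
| 90% | 14.8% | 5.6% |
| 95% | 28.0% | 14.0% |

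**5. If non-significance were read as similarity** (the plan does not say this), for true differences of exactly 7 points:

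| True rates | z test non-significant, 315 / 394 | 90% interval within ±7, 315 / 394 |
|---|---|---|
| 17% vs 10% (either arm worse) | 26.4% / 17.3% | 5.2% / 5.1% |
| 13.5% vs 6.5% | 15.4% / 8.7% | not computed |
| 10% vs 3% | 3.9% / 1.5% | 5.9% / 5.6% |

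**6. Two possible results at 315 per group.**
- 45 vs 32 incomplete (14.3% vs 10.2%): p = 0.11, 90% interval -0.2 to +8.4, 95% interval -1.0 to +9.2. Neither a difference nor equivalence is shown.
- 16 vs 6 incomplete (5.1% vs 1.9%): p = 0.03, 90% interval +0.8 to +5.6. The difference is significant, yet the interval lies wholly inside the limit.

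The test and the interval can thus disagree in either direction, and the plan does not say which one decides.

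**The case against.** The strongest defence is that the parts of an equivalence analysis are already present: the limit, the α and the interval of the difference are all pre-specified, and a sympathetic reader would compare that interval with the only margin in the document. The primary objective is also worded neutrally, as a comparison. But section 7 names the z test as the comparison and adds the interval without a level or any link to 7%, so the reader must supply the rule. That part of the defence does not stand.

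Three narrower points do stand.

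- **The 14.8% is not an error rate caused by the z test.** With 80.1% power, 19.9% of trials miss equivalence anyway, and 14.8% of all trials are misses with a non-significant test. The fix leaves these trials short of equivalence; it only settles what is concluded from them. The figure falls to 5.6% at 394.
- **The 26.4% is conditional** on a reading the plan does not state, and it varies with the rates. At 10% vs 3% the z test passes fewer trials than the interval rule.
- **A 95% interval is a defensible reading**, since incomplete polypectomy is a qualitative variable. It is stricter: at 17% vs 10% it declares equivalence in 2.6% of trials at 315. Its 66.9% power is the low end, because failed cold polypectomies count among the 20% losses but stay in the intention-to-treat analysis, so the number analysed there may lie between 315 and 394.

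**Conclusion.** The concern holds and must be fixed. The named primary test cannot support the equivalence conclusion that the trial was sized for, and no stated rule lets the planned interval do so. This rests on the text and on the exact reproduction of 315 and 394, not on the simulated percentages.

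The clearest numerical consequence is for power at 315 evaluable lesions per group: 80.1% with a 90% interval against 66.9% with a 95% interval, given 10% in both arms and independent lesions. The risk of wrongly claiming similarity (26.4% at 17% vs 10%) arises only if non-significance is read that way. How intention to treat and per protocol are ranked, and how several lesions per patient are handled, are separate questions not judged here.

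**What to change.** In section 7 and the abstract, state:

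> The primary analysis is the two-sided 90% confidence interval of the Cold-minus-Hot difference in the proportion of incomplete polypectomies (two one-sided 5% tests, as in the sample size). Equivalence is concluded only if the whole interval lies within -7 to +7 percentage points. The z test of homogeneity is descriptive.

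This costs wording only: no new data, and 315 and 394 stand.

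If a 95% interval is preferred, keep the same rule and restate power as about 67% at 315 evaluable lesions per group (81% if all 394 are evaluable). Keeping 80% power would need 386 evaluable per group, and 386 / 0.8 = 482.5, so 483 with the same 20% losses.

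The z test may stay as a secondary test of difference, provided the text says that it does not decide equivalence.

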- $^{\fbox{2}}$ Evaluate the factors associated with an incomplete extirpation in each group.
- ² Evaluate the factors associated with a failed cold polypectomy.

4. Design

Randomized clinical trial comparing two endoscopic techniques.

5. Methods

Population to study

The study population includes patients scheduled to perform a colonoscopy in a non-urgent way. The patient will be invited to participate before performing the colonoscopy.

The variables defined in Annex 1 will be collected in a dissociated form database.

Inclusion and exclusion criteria

The inclusion criteria are:

• Patients older than 18 years scheduled to undergo a colonoscopy.

The exclusion criteria are:

- Absence of lesions of 5-9 mm.
- Contraindication for polypectomy (anticoagulant treatment, treatment with clopidogrel, coagulopathy or severe thrombocytopenia)
- Loss of polypectomy specimen
- Refusal to participate

Randomization

It will be done once the patient agrees to participate in the work and the first candidate polyp has been identified. Each patient will be randomized (regardless of the number of injuries per patient) in such a way that all lesions of each patient will be removed in the same way. It will be stratified by endoscopist, in such a way that each endoscopist will have its sequence of sealed randomization. Within each stratum a pure randomization will be carried out through a sequence generated by computer where the probability of belonging to each group will be 0.5. A total of 60 numbered sealed opaque envelopes will be available for each endoscopist that will be stored in the endoscopy room and will be opened consecutively as patients are included.

Intervention

Patients who meet the inclusion criteria and do not present any exclusion criteria (preendoscopic) will be invited to participate in the study. The informed consent will be completed according to the law 41/2002 of autonomy of the patient without it being altered the relationship with your doctor or any damage to your treatment.

1) Endoscopic act

The interventions will be carried out in each of the participating centers. The scans will be performed under sedation according to the protocols established in each center. Once the lesion is identified, the method of extirpation of the lesion will be randomized.

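### No planned primary analysis counts a failed cold-snare attempt against the Cold group, so both analyses could show similarity even if cold snare often fails

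*Combined protocol and SAP*

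**What the plan says.** The primary objective (section 3) concerns the techniques: "To compare the proportion of incomplete polypectomies in both types of polypectomy (cold snare vs. hot snare"). The conceptual hypothesis in section 2 is likewise that cold snare resembles hot snare in incomplete polypectomies.

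Four places bear on a Cold-assigned lesion that is finally removed with hot snare:

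- **Intervention, common evaluation (section 5).** The base is inspected and biopsied after the polypectomies are finished, hence after any change of technique.
- **Statistical analysis (section 7), ITT.** "The analysis will be carried out by intention to treat, regardless of the type of polypectomy performed". The lesion stays in Cold.
- **Statistical analysis (section 7), per protocol.** A Cold-assigned lesion taken out with hot snare is reassigned to Hot.
- **Sample size (section 5).** The loss allowance names unretrieved polyps together with "polypectomies of the failed Cold group of 20"%.

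Failure of cold snare is otherwise addressed only by a secondary objective: "Evaluate the factors associated with a failed cold polypectomy". That is a regression on associated factors, not a comparison between arms.

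**The concern.** The trial aims to show similarity. ITT scores a converted lesion on what remained after the hot resection, so crossover to the comparator pulls Cold towards Hot. A per-protocol analysis is the usual check on such dilution. Here it takes the failures out of Cold and adds them to Hot, so it does not register them either. The two analyses could therefore agree with each other while neither reflects how often cold snare failed to remove the lesion.

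At stake is the wording of the conclusion. A result that supports a strategy of cold snare with hot-snare conversion could be reported as equivalence of the cold technique. The scoring should be settled before the conversion share is known, because choosing it afterwards would be data-driven.

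**Working it through.** **Inputs from the Sample size paragraph.** "Assuming a proportion of incomplete polypectomies in both groups of 10"%; "setting an equivalence limit of 7"% (read as absolute points); "a total of 315 lesions per group are estimated to have an α risk of 5% and a power of 80"%; a 20% loss allowance, giving 394 lesions per group.

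**Input not in the documents.** f, the share of Cold lesions converted to hot snare. It is taken over 0 to 20%. The upper end is the whole loss allowance, which also covers unretrieved polyps and is applied to both arms. It is an outer bound for illustration, not an estimate.

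**1. The plan's own figure.** Take two one-sided tests at 5% each, a true difference of 0, and beta split over both sides (z = 1.645 and 1.282):

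n = (1.645 + 1.282)² × 2 × 0.10 × 0.90 / 0.07² = 314.6 to 314.8 depending on rounding of z, so 315 per group.

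315 / 0.80 = 393.75, so 394. Both stated figures reproduce, and the arithmetic of the sample size is not in question.

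**2. Planned analyses.** Let r be the rate of residual tissue in converted lesions, with 10% in all others.

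- ITT: Cold rate = (1 − f) × 10% + f × r; difference from Hot = f × (r − 10%).
- Per protocol: Cold rate = 10%; Hot rate = (10% + f × r) / (1 + f); difference, Cold minus Hot = f × (10% − r) / (1 + f).

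At r = 10%, both differences are 0 for every f. Equivalence power at 394 per group is 0.90 for ITT. For per protocol it falls only to 0.88 at f = 20% (315 Cold and 473 Hot lesions).

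At r = 0, the ITT Cold rate drops to (1 − f) × 10%, for example 8.0% at f = 20%, which favours Cold. If r exceeds 10%, ITT moves against Cold, but the per-protocol analysis then moves in Cold's favour because the extra events are booked to Hot.

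**3. Counting a conversion as incomplete in Cold.** Cold rate = f + (1 − f) × 10%; difference from Hot = 0.9f, if every Hot lesion is removed as assigned. With a share h of Hot lesions finished by another method, the difference is 0.9 × (f − h).

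| f (assumed) | Cold rate | Difference, h = 0 | Equivalence power, 394 per group |
|---|---|---|---|
| 0% | 10.0% | 0 | 0.90 |
| 2% | 11.8% | 1.8 points | 0.75 |
| 5% | 14.5% | 4.5 points | 0.28 |
| 7.8% | 17.0% | 7.0 points | 0.05 |
| 10% | 19.0% | 9.0 points | under 0.01 |

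The difference reaches the limit at f = 7/0.9 = 7.8%. In lesions, at f = 5%: 0.05 × 394 = 19.7 conversions, plus 10% of the other 374.3 (37.4), gives 57.1 events. ITT at r = 10% gives 39.4.

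These figures treat lesions as independent, as the plan's own calculation does.

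**The case against.** A reader might infer that ITT credits every converted lesion to Cold as a complete resection. The documents do not support that. Each base is biopsied and read centrally, and positive biopsies after conversion still count as incomplete in Cold. Under the 10% assumption about 90% of converted lesions would be scored complete, but none is scored so automatically.

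Keeping converted lesions in the assigned group is also ordinary ITT, and it answers a legitimate question about strategy. The operational hypothesis defines the outcome as residual polypoid tissue, and failed cold polypectomy is a separate concept. Combining the two makes a composite, and the 7-point limit and 10% rate were set for residue detected by biopsy. This is a good reason not to make agreement of the composite a condition for claiming equivalence: power would fall from 0.90 to 0.75 at f = 2% and to 0.28 at f = 5%.

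The sample-size paragraph can be read consistently with section 7 if failed Cold lesions are losses to the per-protocol Cold set only. Then 394 × 0.80 = 315.2 protects that set. Striking them from the allowance would remove the protection, so they should stay there with their scope stated.

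Finally, the supplied text contains no definition of a failed cold polypectomy. Annex 1, which defines the variables, is not in it and may contain one.

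These points limit the remedy. They do not supply a planned primary analysis in which failure of cold snare counts against Cold, and the objective as written is about the technique.

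**Conclusion.** The point holds as a gap in what the planned comparison can show. A converted Cold lesion is scored on later biopsies in ITT, passed to the comparator per protocol, and called a loss in the sample size. No primary analysis records the failed cold attempt.

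The size depends entirely on f: 0.9f points, or 1.8 at 2%, 4.5 at 5% and 7.0 at 7.8%, assuming 10% residue otherwise and no comparable failures in Hot. If conversions are rare, the effect is small. A reader might take the 20% allowance as the expected failure rate of cold snare. The text does not support this, because the figure is shared with unretrieved polyps and applied to both groups. Nor do the documents show that cold snare fails often. They show only that, if it did, the planned primary analyses need not reveal it.

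The scoring of a converted lesion under ITT is inferred from the timing of the biopsies and the ITT rule together. The plan does not state it outright.

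**What to change.** 1. Keep the ITT analysis as planned, and state that a converted lesion is scored in its assigned group on its post-conversion biopsies.
2. Define failed cold polypectomy for analysis purposes, and report the share of Cold lesions converted with its confidence interval.
3. Pre-specify a supportive analysis by assigned group, on the same lesions, counting any lesion not removed with its assigned technique as incomplete. Apply it symmetrically in both arms and show its confidence interval beside the primary result.
4. Do not treat the analysis that moves converted lesions to Hot as confirmation of similarity.
5. If the supportive analysis differs from the primary one, word the conclusion as applying to cold snare with hot-snare conversion. Do not make agreement a mandatory gate.
6. Reconcile the Sample size paragraph with section 7: failed Cold lesions are losses to the per-protocol Cold set, not to ITT.

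The cost is some SAP wording and one extra analysis on data that the failed-cold objective already requires. The downside is a possibly narrower claim for the cold technique.

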- Cold Group: polypectomy with a cold snare will be carried out according to the usual standards recommended by international societies. As far as possible we will try to arrange the lesion in the position equivalent to 5 o'clock on the dial, the end of the snare will be placed several millimeters from the lesion and the tip of the catheter will be angled downwards as the Asa, without aspiration at any time to avoid entrapment of the submucosa.
- -Hot Group: polypectomy with snare connected to the electrosurgical unit according to the standards recommended by international societies, using a mixed current (cut-coagulation). Once the lesion is captured, the snare is pulled to slightly separate it from the surrounding mucosa before polypectomy. Elevation of the lesion prior to polypectomy will not be performed.
- -Common evaluation: once the polypectomies are completed, the basis of the polypectomies will be evaluated, taking biopsies from any suggestive area and also 2 random biopsies at the base of the polypectomy.

2) Postendoscopic follow-up

After a minimum of 21 days and a maximum of 28 days from the endoscopic examination, the patient will be contacted by telephone to collect the form about the evolution of the abdominal symptoms and to collect data about the appearance of complications (questions will be asked about visits to the hospital and in a targeted manner about the most frequent symptoms of the usual complications (fever, hemorrhage, abdominal pain).

3) Histological analysis

The analysis of the specimens of the polypectomies will be carried out in each center according to their usual protocol. The analysis of the biopsies of the base of the polyp will be carried out centrally by a pathologist with more than 5 years of experience in digestive pathology. Samples from the base of the polyp will be sent biweekly from each center to the university health care complex in Salamanca through a messenger service. The pathologist will be blinded regarding the histological diagnosis of the excised polyp and the type of polypectomy (although it is true that it is difficult to blind this last point since the presence of heat artifacts in those removed with a hot handle is very frequent). The samples sent for centralized analysis will not be conserved, but will be destroyed once the study is completed according to the usual protocols.

Sample size

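### The 'per protocol' analysis is an as-treated regrouping that moves converted Cold lesions into Hot, and the plan does not say whether it or ITT decides the primary objective

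*Combined protocol and SAP*

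**What the plan says.** - Section 7 (Statistical analysis) plans two analyses of the primary objective. The first: "The analysis will be carried out by intention to treat, regardless of the type of polypectomy performed". The second: "per protocol (assigning the lesions assigned to the group Cold that are extirpated with hot snare to the Hot group". Only Cold-to-Hot movement is described.
- The Abstract pairs them without ranking: "The analysis will be carried out by intention to treat and by protocol". No other section says which one decides or what follows if they disagree.
- Section 5, Randomization, makes the patient the randomised unit, so that "all lesions of each patient will be removed in the same way".
- Section 5, Sample size, sets a 7% equivalence limit with 10% incomplete in both groups. Its loss allowance reads "Assuming a proportion of losses (polyps not recovered for histological study, polypectomies of the failed Cold group of 20" (per cent). Section 3 has a secondary objective: "Evaluate the factors associated with a failed cold polypectomy". Neither section defines a failed cold polypectomy as one removed with a hot snare.
- Section 5, Intervention, takes the outcome biopsies late: "once the polypectomies are completed, the basis of the polypectomies will be evaluated". The biopsy result of a converted lesion therefore reflects its final, hot-snare removal.

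**The concern.** A per-protocol set normally keeps the lesions treated as assigned and drops the rest. The rule in Section 7 instead analyses lesions by the technique finally used. Converted lesions are selected after randomisation by how the cold technique performed. If they differ from other lesions, the rule alters both groups at once: it removes them from Cold and adds them to Hot. Because single lesions move while patients are randomised, one patient can contribute to both groups.

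The trial is sized for equivalence, so the choice of analysis set can change the conclusion. With two unranked analyses, the plan has no answer when they disagree, and the choice could be made after the results are seen.

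**Working it through.** **1. The plan's own figure.** For equivalence of two proportions with p = 0.10, limit 0.07, 5% for each one-sided test and 80% power: n = 2p(1-p)(z0.95 + z0.90)²/0.07² = 2 × 0.10 × 0.90 × (1.645 + 1.282)²/0.0049 = 314.6 with unrounded quantiles, so 315. Then 315/0.8 = 393.75, so 394. Both stated figures reproduce. The match implies a 90% interval, which is assumed below because Section 7 gives no level.

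**2. Algebra.** Let pC and pH be the ITT incomplete rates, f the share of Cold lesions converted, and h the incomplete rate in converted lesions. Arms are of equal size.

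- Remaining Cold: q = (pC - f·h)/(1 - f)
- Regrouped Hot: (pH + f·h)/(1 + f)
- Shift of the regrouped difference from ITT: f[(q - h) + (pH - h)/(1 + f)]

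Both terms vanish only if h equals both q and pH; otherwise they can only cancel by coincidence. Exclusion compares q with pH and carries only the first term.

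**3. Inputs.** f and h are assumptions. The documents offer two biopsy-based reference points for h. Section 1 gives 6.8% for each snare: for hot, "All resections were made with hot loop, being incomplete in 6.8% of the lesions <10 mm"; for cold, 59 smaller polyps averaging 3.7 mm. Sample size assumes 10%. The 20% value is an assumption beyond these.

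**4. Both arms at 10% under ITT.** Verdicts come from 400,000 simulated trials per scenario, with independent lesions and equivalence declared when the 90% Wald interval lies inside ±7 points. Paired figures are for 315/394 lesions per arm.

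| f | h | q | Regrouped Hot | Shift (points) | ITT and regrouped verdicts opposite | Same f, h = 10% (chance) |
|---|---|---|---|---|---|---|
| 10% | 6.8% | 10.36% | 9.71% | +0.6 | 14%/9% | 12%/7% |
| 10% | 10% | 10.00% | 10.00% | 0 | 12%/7% | 12%/7% |
| 5% | 20% | 9.47% | 10.48% | -1.0 | 16%/11% | 9%/5% |
| 10% | 20% | 8.89% | 10.91% | -2.0 | 31%/24% | 12%/7% |

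Example, last row: q = (0.10 - 0.02)/0.90 = 0.0889; Hot = (0.10 + 0.02)/1.10 = 0.1091; difference -0.0202. Exclusion gives 0.0889 - 0.10 = -0.0111.

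**5. Cold 17%, Hot 10% (a true deficit at the limit).** ITT declares equivalence in about 5%.

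| f | h | q | Regrouped Hot | Difference (points) | Regrouped declares equivalence |
|---|---|---|---|---|---|
| 10% | 6.8% | 18.13% | 9.71% | 8.4 | 2%/1% |
| 10% | 17% | 17.00% | 10.64% | 6.4 | 8%/9% |
| 10% | 20% | 16.67% | 10.91% | 5.8 | 12%/13% |

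In the middle row converted lesions match the rest of Cold, yet the 7.0-point deficit shrinks to 6.4 because Cold-type results are added to Hot.

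**6. Sensitivity case only: h = 30%, f = 10%.** At 17% vs 10%, the regrouped analysis declares equivalence in 32%/37% and exclusion in 14%/15%. With a 95% interval the regrouped figure is 20%/26%. At equal 10% rates the shift is -4.0 points with regrouping and -2.2 with exclusion.

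**The case against.** Three defences carry weight.

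- *The rule is disclosed and ITT is intact.* The regrouping is spelled out beside its label, ITT is listed first, and relabelling alone changes no number. This stands as far as it goes, but it does not supply a deciding analysis.
- *At document-based rates the harm is small.* With converted lesions at 6.8%, opposite verdicts exceed chance by about 2 points, and at 17% vs 10% the regrouping is conservative. This stands. Figures near 30% or above in Section 1 come from assessing resection margins, not from the biopsy method used here, so the 30% case should not carry the point.
- *The verdicts rest on a rule the plan lacks.* Section 7 gives a z test and an interval of unstated level, and links neither to the 7% limit. This stands; the verdict percentages are modelled, while the shifts do not depend on the interval.

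A reader might also infer more than the documents support:

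- *That Sample size contradicts Section 7.* A loss allowance is not an analysis rule. Planning for about 315 Cold lesions to remain after failures leave Cold is compatible with the second analysis; ITT simply keeps more. The wording needs clarifying, no more.
- *That the regrouping always favours Cold.* The sign depends on h, and at 6.8% with equal arms it goes the other way.
- *That incomplete rates above 6.8% have no basis in the documents.* Sample size assumes 10% by biopsy. What is missing is a rate for converted lesions.

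**Conclusion.** The point holds and should be fixed. The second primary-objective analysis is as-treated, is labelled per protocol, covers conversions in one direction only, and is not ranked against ITT. These facts are read from the text and need no assumption.

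The size is uncertain. For conversion of 5% to 10% and incomplete rates of 6.8% to 20% in converted lesions, the shift at equal 10% rates runs from +0.6 to -2.0 points against a 7-point limit. The verdict figures further assume a 90% interval, independent lesions and 315 or 394 per arm. Nothing here shows that the ITT result would be invalid.

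**What to change.** Change the analysis wording before results are seen:

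1. Define per protocol as lesions removed with the assigned technique. Exclude converted Cold lesions and do not add them to Hot.
2. Relabel the regrouped comparison *as treated, exploratory*.
3. State that ITT decides the primary objective, with per protocol as support.
4. Report the number of converted lesions and their incomplete rate.
5. In Sample size, clarify whether a failed Cold polypectomy means one removed with a hot snare, and that such lesions stay in Cold under ITT.

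Requiring equivalence in both ITT and the exclusion-based set is an optional trade-off, not a free safeguard. At equal 10% rates, power falls from about 80%/90% (ITT alone, 315/394 per arm) to about 75%/86% (5% converted at 20%), 69%/81% (10% at 20%) or 57%/69% (10% at 30%).

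The cost is a smaller Cold per-protocol set: 394 × 0.95 = 374 lesions at 5% converted or 394 × 0.90 = 355 at 10%, before other losses. Exclusion reduces the selection bias but does not remove it: -1.1 instead of -2.0 points at 10% converted and 20% incomplete. The secondary objective on failed cold polypectomy suggests the data will be collected; confirm this against the variable list in Annex 1, which is not in the text reviewed.
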